2.2 Secondary Objective(s)

2.2.1 Clinical:

- To evaluate whether PN OIT induces increased tolerance, defined as a statistically significant increase in the median eliciting dose (ED) from DBPCFC1 to DBPCFC3.
- To evaluate whether PN OIT induces clinical desensitization, defined as 1) a median 10-fold or greater increase in ED from DBPCFC1 to DBPCFC2; 2) a statistically significant higher median ED at DBPCFC2 between active and control treatment; and 3) a significantly lower frequency of accidental ingestion reactions in active versus control treatment.
- To evaluate the safety of PN OIT.

2.2.2 Mechanistic:

- To determine whether PN OIT induces a statistically significant increase in the TCR clonal diversity of Treg
 populations during active treatment among participants who achieve increased clinical tolerance (Tolerance
 and Partial Tolerance Groups as defined in clinical endpoints) versus the Treatment Failure Group.
- To determine whether PN OIT suppresses mast cells by inducing a significant suppression of the median ED on end-point dilution skin testing in actively treated participants by the end of maintenance therapy.
- To determine whether PN OIT suppresses basophils as defined by a 10-fold suppression of peanut-specific basophil ED in actively treated participants by end of maintenance.
- To determine whether either mast cell or basophil suppression at the end of maintenance therapy is significantly associated with clinical outcomes following avoidance.

2.2.3 Exploratory:

- To describe the gene expression profiles and clonal diversity of regulatory and effector T cell subsets before
 and after OIT to better understand the phenotype and ontogeny of these subsets and potentially discover
 new therapeutic pathways.
- To engineer human MHC class II tetramers on common HLA backgrounds and map T cell epitopes of the dominant peanut allergens for use in validating earlier findings and for future studies of peanut-specific immune responses in humans.
- To determine whether microbial dysbiosis is associated with the development of desensitization, oral tolerance, or persistent gastrointestinal adverse events while on oral immunotherapy.

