7.4.5 Double-Blind Placebo-Controlled Food Challenge 2 (Day 434)

After taking maintenance dose for 12 weeks, participants will come to MGH CRC for their second double-blind, placebo-controlled food challenge (DBPCFC2).

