If the participant has a Build Up dose in the MGH CRC and experiences symptoms that require treatment in accordance with Figure 15.4, the patient will continue on the previously tolerated dose for the next two week interval.

Participants may also develop symptoms during the subsequent at home administrations of the Build Up doses. The participants will be instructed to contact study staff for any symptoms. The study physician's judgment will be required to determine the best course of action with possible actions being the following:

- 1. Continue with daily home dosing at the current Build Up dose
- 2. Continue with daily home dosing at the previously tolerated daily dose for the next (additional) 2-week interval
- 3. Return the following day to the MGH CRC for repeat trial at the current Build Up dose
- 4. Return the following day to the MGH CRC for dosing at a previously tolerated dose
- 5. Discontinue dosing

For reactions for which epinephrine was given (1-2 doses) or was indicated (as outlined in Figure 15.4), treatment will be withheld until it can be resumed (as below) in the MGH CRC. As per individual stopping rules (see section 8.1.2) participants who receive more than two doses of epinephrine for a single reaction will be withdrawn. For minor reactions (appropriately treated without epinephrine as outlined in Figure 15.4), treatment will be resumed at home unless the study physician determines that resumption should take place in the CRC.

Resumption of treatment will proceed as follows: 50% of the previously tolerated amount for 4-5 days, 75% for 4-5 days and then 100%. The previously scheduled Build Up visit will be postponed to take place 2 weeks (12 days minimum) after resumption of the 100% dose.

If a participant fails to tolerate 3 consecutive Build Up attempts prior to reaching 600 mg or if the participant fails to reach 600 mg by week 50, then the participant will be considered a treatment failure.

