If the participant misses one or two days of the daily dose for any reason then he or she will continue on the same dose. If the participant misses the dose for three days, the participant will be asked to return to the MGH CRC for the next daily dose to ensure that there are no adverse effects from resuming dosing. If the participant misses their dose for four or more days, he/she will have to return to the MGH CRC for a modified rush protocol to escalate back to the highest previously tolerated dose beginning at 50%. For the duration of the study, the participant will be asked to continue to follow a peanut elimination diet.

7.7.2.3 Maintenance At the end of the Build Up phase, the participants will continue on the achieved daily dose for 12 weeks in the maintenance phase. Participants in a reported study have tolerated a very similar dosing schedule with minimal symptoms [?]. Participants will enter the Maintenance phase at the highest dose tolerated by week 50 (at least 600 mg).

Participants may develop symptoms during the at home administrations of the Maintenance doses. The participants will be instructed to contact study staff for any symptoms. The study physician's judgment will be required to determine the best course of action with possible actions being the following:

- 1. Continue with daily home dosing at the current Maintenance dose
- 2. Continue with daily home dosing at 50% of the Maintenance dose
- 3. Return the following day to the MGH CRC for observed trial at the current Maintenance dose
- 4. Return the following day to the MGH CRC for observed trial of a reduced dose (e.g. 50%, 75%)
- 5. Discontinue dosing

For reactions for which epinephrine was given (1-2 doses) or was indicated (as outlined in Figure 15.4), treatment will be withheld until it can be resumed (as below) in the MGH CRC. As per individual stopping rules (see section 8.1.2) participants who receive more than two doses of epinephrine for a single reaction will be withdrawn. For minor reactions (appropriately treated without epinephrine as outlined in Figure 15.4), treatment will be resumed at home unless the study physician determines that resumption should take place in the CRC.

Resumption of treatment will proceed as follows: 50% of the previously tolerated amount for 4-5 days, 75% for 4-5 days and then 100%. The previously scheduled Build Up visit will be postponed to take place 2 weeks (12 days minimum) after resumption of the 100% dose.

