9.2.2 Study Participant Populations

As described above, the per protocol sample will consist of all active treatment participants completing DBPCFC3.

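### Desensitization criteria 1 and 2 rest on a DBPCFC2 eliciting dose that active participants supply only after passing build-up, so they barely register build-up failure

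*Combined protocol and SAP*

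**What the plan says.** Section 2.2.1 gives desensitization three parts. The first two use the challenge: "a median 10-fold or greater increase in ED from DBPCFC1 to DBPCFC2; 2) a statistically significant higher median ED at DBPCFC2 between active and control". The third does not: "and 3) a significantly lower frequency of accidental ingestion reactions in active versus control treatment". Section 3.1.2 also lists the change in median ED from DBPCFC1 to DBPCFC2 as a secondary endpoint in its own right.

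Sections 3 and 7.4.5 place DBPCFC2 after 12 weeks of maintenance. Section 7.7.2.3 sets the entry condition: "Participants will enter the Maintenance phase at the highest dose tolerated by week 50 (at least 600 mg". Section 7.7.2.2 adds that "if the participant fails to reach 600 mg by week 50, then the participant will be considered a treatment failure". Other participants can leave at the modified rush (7.7.2.1) or under the individual stopping rules (8.1.2). For none of them does the plan describe a DBPCFC2 or assign an ED. Section 9.1 counts all 10 placebo participants after DBPCFC2.

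On analysis sets, 9.2.2 says only that "the per protocol sample will consist of all active treatment participants completing DBPCFC3". Section 9.2.5 names a modified-rush population for the Tolerance outcome, and it excludes missing data for immune and mechanistic outcomes. Neither rule is extended to the DBPCFC2 ED. By contrast, failure to reach 600 mg does count as Treatment Failure in 3.1.1 and 9.2.4.1.

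**The concern.** Reaching DBPCFC2 is itself a result of treatment in the active arm. A participant whose baseline ED was at most 443 mg (4.1) and who now takes hundreds or thousands of milligrams a day is already most of the way to a 10-fold rise. Participants who could not build up have no value and drop out of both medians. In the placebo arm nothing comparable removes the most reactive participants.

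Criterion 2 is then not a comparison of the randomised arms, and criterion 1 describes only those for whom build-up worked. The risk is that a trial in which most of the active arm fails build-up would still satisfy both challenge-based criteria and show a large ED change on the 3.1.2 endpoint.

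**Working it through.** **Anchor.** The documents give no power or error rate for these criteria. The nearest stated figure is the primary Treg test in 15.6. A two-sided t test (noncentral t, alpha 0.05) with 8 v 14 at 1.5 SD gives 0.896, against the stated 0.90. All 18 cells of that table reproduce within 0.5 percentage points. The planned 75% desensitized (15.5) is 0.75 × 30 = 22.5, taken as 22, which leaves about 8 of 30 not desensitized.

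**Inputs from the documents.** 30 active and 10 placebo (9.1); baseline ED at most 443 mg (4.1); cumulative DBPCFC2 steps 3, 13, 43, 143, 443, 1443 and 4443 mg (7.7.1).

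**Assumptions.**
- Baseline ED is log-normal with median 45 mg and interquartile range 4.5 to 200 mg, truncated at 443 mg. Section 1.6.1 cites these figures for the oldest group in a study of children, not for this trial. They put about 83% of participants at 143 mg or less.
- Criterion 2 uses a two-sided Mann-Whitney test at 0.05. The plan names no test.
- Active completers react at 1443 or 4443 mg, and placebo stays at baseline.

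**Criterion 1, arithmetic only.** 1443/143 = 10.1, 1443/443 = 3.3 and 4443/443 = 10.03. If completers react at 1443 mg or above, criterion 1 fails only when about half or more of them started at 443 mg and reacted at 1443 mg.

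**Criterion 2, exact.** With m active completers all above 10 placebo participants, p = 2/C(m+10, 10).
- m = 1: 2/11 = 0.18
- m = 2: 2/66 = 0.030
- m = 3: 2/286 = 0.007

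Two completers out of 30 are enough; one is not.

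**Both criteria, simulated.** The last column counts all 30 active participants and keeps failures at baseline ED.

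| Build-up failures of 30 | Completers only | All 30 counted |
|---|---|---|
| 8 | 1.00 | 1.00 |
| 12 | 1.00 | 0.86 |
| 14 | 1.00 | 0.31 |
| 15 | 1.00 | 0.005 |
| 16 | 1.00 | 0.00 |
| 20 | 1.00 | 0.00 |
| 27 | 0.99 | 0.00 |
| 28 | 0.98 | 0.00 |
| 29 | 0.00 | 0.00 |

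If every completer reacts at 1443 mg, the completer-only figure is 0.93 at 27 failures. Counting all 30 then gives 0.94 at 8 failures, 0.05 at 14 and 0.00 at 15. The drop at 15 is mechanical: the median of 30 becomes the average of 1 and the smallest completer fold change x, and (1 + x)/2 ≥ 10 needs x ≥ 19.

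**No treatment effect.** Here the result depends on how many people lose reactivity spontaneously, which the documents do not give.
- No loss, test-retest noise of 0.3 log10: criterion 1 is met in about 4% of trials and criterion 2 in about 10%.
- 2% loss in both arms: both met in 10 to 17%.
- 5% loss: both met in 35 to 43%.
- 10% loss: both met in 61 to 70%.

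With all 30 counted, both are met in 0% of trials at 5% and 10% loss, and criterion 2 alone in 2 to 3%.

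**Criterion 3.** Assuming Fisher's exact test on participants with a reaction, 30 v 10, it is met with probability 0.01 to 0.02 at equal rates. With no reactions at all in the active arm, it is met with probability 0.07, 0.32, 0.62 and 0.95 at placebo rates of 10%, 20%, 30% and 50%.

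**The case against.** A reader might infer that the whole desensitization rule is met whatever share of the active arm fails. The documents do not support that. Criterion 3 is joined to the others by *and*, uses a different outcome, and would be met by chance in only 1 to 2% of no-effect trials. The null rates above are therefore not false-positive rates for the overall conclusion. Nor does *whatever share* hold literally, since a single completer cannot reach significance on criterion 2.

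A reader might also infer that only successes enter the active side, or that every active value is at least 1443 mg. Sections 3.1.1 and 5.6.1 expressly foresee an ED below 1443 mg at DBPCFC2, and 7.7.2.3 allows home dosing at half the maintenance dose. The 1443 mg floor appears only if the DBPCFC3-completer sample is borrowed. That sample is defined for the Treg hypothesis and contains no placebo participants, so criterion 2 could not be run on it.

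Three further points stand. The restriction to completers is inferred from the visit flow; nothing expressly bars a build-up failure from the challenge. The trial selects for persistent allergy (1.2) and counts every placebo participant as a failure after DBPCFC2, so appreciable spontaneous loss is not the plan's own expectation. Section 9.2.5 requires discontinuations to be tabulated, so a collapse of the active arm would be visible.

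None of this removes the selection. No rule scores the absent values, and a discontinuation table does not alter the criteria. Criterion 3 gives no protection to the stand-alone ED endpoint in 3.1.2.

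**Conclusion.** The point holds for criteria 1 and 2 and for the DBPCFC1-to-DBPCFC2 ED endpoint. It does not extend to the three-part rule as a whole. Following the visit flow, the active side is conditioned on reaching 600 mg and completing maintenance, and the placebo side is not. The two criteria then hardly respond to the build-up failure share up to 28 of 30.

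The fold ratios and exact p-values need no distributional assumption beyond full separation. The simulated probabilities rest on the borrowed baseline distribution, the assumed test and the assumed completer EDs. The null rates rest on an assumed loss rate and should be read only as a range.

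At the planned 75% desensitized, counting everyone leaves criteria 1 and 2 met. The two approaches part as failures approach half the arm. This concerns a secondary objective and should be corrected before analysis; it does not touch the primary Treg comparison.

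**What to change.** In 2.2.1 and 3.1.2, state that criteria 1 and 2 and the DBPCFC1-to-DBPCFC2 ED change are evaluated in all randomised participants by assigned arm.

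- Score a participant with no DBPCFC2 because of a failed modified rush or build-up, dosing reactions or treatment-related withdrawal as not desensitized: DBPCFC1 ED carried forward, fold change 1.
- Score clearly unrelated missingness, such as pregnancy or loss to follow-up, the same way, and add a sensitivity analysis, because baseline ED is a convention there rather than an observed failure.
- Name a rank test between arms for criterion 2.
- Report completer medians as supportive, beside the share of the randomised active arm that reached DBPCFC2.
- If build-up failures are meant to be challenged at DBPCFC2, the visit sections should say so.

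The cost is wording only, with no new data. Reported medians will be somewhat less favourable. At 8 failures of 30, criteria 1 and 2 are still met with probability 0.94 to 1.00 under the assumptions above.

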1.6 Risks

1.6.1 Risks of Investigational Product(s) / Intervention(s)

In previous studies of peanut oral immunotherapy, mild to moderate side effects of dose increases (done at study visits) have included: lung symptoms (e.g., cough, increased use of albuterol for individuals with asthma), GI tract symptoms (nausea, vomiting, diarrhea), skin symptoms (hives, itchiness) and nose symptoms (e.g. stuffiness) More rarely, similar side effects have also occurred during doses taken at home, especially when the child had an intercurrent illness (e.g., a cold), exposure to another allergen (e.g., during pollen season for those who have seasonal allergies), in association with exercise or when taken on an empty stomach [? ?]. Menses together with exercise has also been reported in one case as a potential co-factor for reactions to OIT [?]. Additional rare risks of OIT and food challenges are those of anaphylaxis and include respiratory obstruction (e.g., wheezing, coughing, and swelling of the voice box) and cardiovascular problems such as a drop in blood pressure or cardiovascular collapse. Most OIT studies to date have targeted a younger patient population. A 2011 study [?] of children aged 3 to 18 noted that peanut allergic patients over 10 years of age reacted at lower eliciting doses than those in the youngest tertile (< 5.5 years). They did not attempt to report on reaction severity. The median eliciting dose for the oldest age group was approximately 45 mg of peanut protein with an interquartile range of 4.5 to 200 mg peanut protein. In a study of the efficacy of anti-lgE for the treatment of adolescents and adults (13-59 years) with peanut allergy, the mean pre-treatment eliciting dose was 330 mg of peanut flour (range 1 - 2000 mg) [?].

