3 STUDY DESIGN

This is a phase I/II double-blind placebo-controlled interventional study of peanut allergen oral immunotherapy (OIT) for adolescents and adults (7 to 55 years of age) with IgE-mediated allergy to peanut (evidence of sensitization and demonstrated clinical reactivity). The major objective of this study is to provide additional safety and mechanistic data on OIT for people with IgE-mediated peanut allergy.

There will be 3:1 active to placebo randomization. The treatment substance is peanut flour. The placebo is roasted oat flour. An schematic of the design is presented in Figure 15.1. See Appendix 16.1 for schedule of study events.

Clinical assessments will be made by double-blind placebo-controlled food challenge at baseline (DBPCFC1), after 12 weeks of maintenance therapy (DBPCFC2) and then after an additional 12 weeks off therapy while strictly avoiding dietary peanut protein (DBPCFC3). Participants who do not react at \geq 443 mg of peanut protein (cumulative) during DBPCFC1 will be excluded from the study.

18 of 68

AADCRC Protocol 2012P002153

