3.1.2 Secondary Endpoint(s)

Secondary endpoints are:

Clinical:

- Tolerance:
 - The change in median eliciting dose (ED) from DBPCFC1 to DBPCFC3.
- Desensitization:
 - The change in median eliciting dose (ED) from DBPCFC1 to DBPCFC2.
 - The frequency of accidental ingestion reactions in active versus control treatment.
- Safety:
 - Anaphylaxis requiring more than 1 administration of epinephrine; or hospitalization.
 - Death as a result of the investigational product.
 - The rate of reported adverse advents due to accidental ingestions in the active versus placebo groups.

Mechanistic:

- The change in the TCR clonal diversity of in vitro allergen-expanded Treg cells and induced Treg cells measured by TCRβ CDR3 sequence clonotyping of sorted cells during active treatment among participants who achieve increased clinical tolerance (Tolerance and Partial Tolerance Groups as defined in clinical endpoints) versus the Treatment Failure Group.
- The change in ED of end-point dilution skin testing between actively treated and placebo treated participants following maintenance therapy.
- The change in ED of end-point dilution skin testing among actively treated participants following maintenance therapy and avoidance between clinical outcome groups.

- The change in peanut-specific basophil ED in actively treated participants at the end of maintenance and the end of avoidance between clinical outcome groups.
- The change in peanut allergen-specific IgG4 in actively treated participants by the end of maintenance between clinical outcome groups.
- The change in Ara h 2 specific surface and secreting B cells between baseline (measured after 12 weeks
 of treatment) and the end of maintenance.
- Statistically significant gene expression changes by transcriptional profiling of regulatory and effector T cell participants before and after OIT between clinical outcome groups.

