7.4 Main Study Visits

7.4.1 Double-Blind Placebo-Controlled Food Challenge 1 (Day 28)

Participants will come to the MGH CRC four weeks (± 4 days) after the baseline visit for a double-blind, placebo -controlled food challenge (DBPCFC1) to peanut. In a DBPCFC, two challenges, one containing placebo material (toasted oat flour) and one containing peanut flour will be performed on two days within a two week period. The order of challenge will be determined by coin toss by the dietitian and will be unknown to the study nurse, investigator, and study participant. The MGH CRC dietician will prepare the challenge materials. Details of the DBPCFC procedure are below in section 7.7.1.

Prior to each challenge, the participant will have a physical exam with vital signs, spirometry, and an IV will be placed. A negative urine pregnancy test will be documented for female participants of child-bearing potential; if the test is positive, the visit will be cancelled and if pregnancy is confirmed, the subject will be withdrawn from the study. The participant will be required to have a baseline FVC and FEV1 >80% of their predicted values and an FEV1/FVC of >0.7 or the DBPCFC will be rescheduled. A study nurse who is blinded to the testing material will administer the challenge. The supervising physician will be present during the challenge and will also be blinded to testing material.

A member of the study staff will follow up with participant with a telephone call the day after the DBPCFC for active safety monitoring.

If the participant reacts at the 300 mg dose of peanut protein or less (443 mg cumulative), he/she will be randomized to receive active or placebo OIT.

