9 SAMPLE SIZE CALCULATIONS AND STATISTICAL PLAN

9.1 Sample Size and Power Calculations

As the hypothesis regarding Treg induction and clonal tolerance can only be defined among those individuals who achieve desensitization and go on to DBPCFC3, the analysis will be per protocol for those participants who complete both post treatment challenges. The difference in the proportion of Treg will be compared between the groups using Students t test for comparison of means. Because we are expecting the primary outcome variable (difference in the proportion of Treg) to be log-normally distributed, we plan to carry out the t test on the log transformed variable. We will be powered at the expected effect on Treg if as few as six individuals (20% clinical effect and 10% dropout) who complete the protocol achieve our defined measure of at least partial clinical tolerance. Table 15.6 shows power calculations around these assumptions using a two sided t test at an alpha level of 0.05.

The sample size selected is 30 active treatment and 10 placebo treatment. We are applying the following assumptions for our power analysis (see Figure 15.5 for schema of assumptions).

- Approximately 27% of the Active Treatment group (8/30) will achieve Partial Tolerance (ED at DBPCFC3 <4430 mg but ≥430 mg AND >10-fold more than at DBPCFC1) or Full Tolerance (no reaction at DBPCFC3).
- The comparison of interest is between the combined Tolerance/Partial Tolerance and Active Treatment Failure groups who complete DBPCFC3.
- Those who fail to become desensitized after active treatment and those who receive placebo treatment are not fully informative for the primary endpoint and are therefore excluded for the per protocol analysis.
- The difference from baseline to the end of maintenance therapy in the mean proportion of induced Treg (CD45RA- CD25++ FoxP3++ of CD4+ T cells) between the Tolerance/Partial Tolerance and Treatment Failure groups will be 1.5 times the standard deviation.

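### The only between-arm test of food-challenge eliciting dose compares DBPCFC2 without the DBPCFC1 dose that every randomised participant has; with 30 v 10 this costs precision, not validity.

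*Combined protocol and SAP*

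**What the plan says.** Section 2.2.1 requires three things for desensitization: "a median 10-fold or greater increase in ED from DBPCFC1 to DBPCFC2"; "a statistically significant higher median ED at DBPCFC2 between active and control treatment"; and fewer accidental-ingestion reactions on active than on control. The second is the only one that compares ED between the randomised arms, and it looks at DBPCFC2 alone. Section 3.1.2 lists "The change in median eliciting dose (ED) from DBPCFC1 to DBPCFC2" as the desensitization ED endpoint, with no mention of the control arm or of adjustment.

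Section 7.4.1 makes a DBPCFC1 reaction a condition of randomisation: "If the participant reacts at the 300 mg dose of peanut protein or less (443 mg cumulative), he/she will be randomized". The baseline ED is therefore complete. Section 7.7.1 gives DBPCFC2 the same dose steps plus two more, up to 4443 mg cumulative.

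Section 9.1 states: "The sample size selected is 30 active treatment and 10 placebo treatment". Section 9 specifies a t test for log-transformed Treg and no test, model or covariate for any ED comparison. Sections 7.1 and 7.8.1 describe 3:1 allocation with no stratification by baseline sensitivity.

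**The concern.** Baseline challenge sensitivity appears to vary widely. For the oldest group in a cited paediatric study, section 1.6.1 gives a median ED of "approximately 45 mg of peanut protein with an interquartile range of 4.5 to 200 mg peanut protein". If a participant's DBPCFC1 ED predicts the DBPCFC2 ED at all, a comparison that ignores it carries avoidable noise. With only 10 placebo participants, a chance difference in baseline sensitivity between the arms would also show up partly as a difference at DBPCFC2. Since desensitization needs this test to be significant, avoidable noise raises the chance of missing a real effect. The covariate is already collected on everyone.

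**Working it through.** **Plan's own figure.** The documents give no power for the ED comparison. The nearest figure is in Table 15.6 (Treg, 8 v 14, 1.5 SD, two-sided 0.05): stated 0.90, and 0.896 from the noncentral t distribution. All 18 cells reproduce within 2 points, so the same method is used in step 3.

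**1. Baseline spread.** Taking the section 1.6.1 figures as log-normal, SD of log10 ED = log10(200/4.5)/1.349 = 1.648/1.349 = 1.22. Truncating at the 443 mg entry limit reduces it to 0.93.

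**2. Chance imbalance at 30 v 10.** SE factor = sqrt(1/30 + 1/10) = 0.365. One SD of imbalance in mean baseline log ED = 0.93 × 0.365 = 0.34 log10, a ratio of 10^0.34 = 2.2. With equal SDs at the two challenges, the share that carries into DBPCFC2 is rho × 0.34. At rho 0.5 that is 0.17 log10, or 10^0.17 = 1.5-fold. The chance that the arms differ at baseline by more than 0.5 SD is 2[1 − Φ(0.5/0.365)] = 2[1 − Φ(1.37)] ≈ 0.17.

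**3. Closed form.** Adjustment multiplies the residual variance by 1 − rho². Rho is assumed.

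| rho | 1 − rho² | SE (in SD) | equivalent placebo n at 3:1 | power at 1.0 SD |
|---|---|---|---|---|
| unadjusted | 1 | 0.365 | 10 | 0.76 |
| 0.3 | 0.91 | 0.348 | 10/0.91 = 11.0 | 0.80 |
| 0.5 | 0.75 | 0.316 | 10/0.75 = 13.3 | 0.87 |
| 0.7 | 0.51 | 0.261 | 10/0.51 = 19.6 | 0.96 |

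A 10-fold effect is 1 log10, i.e. 1/0.93 = 1.08 SD or 1/1.22 = 0.82 SD. The closed form is optimistic because the dose steps are coarse. A rho of 0.5 on the underlying scale becomes about 0.44 on the observed steps, or about 0.36 if it applies before the eligibility cut. The variance reduction is then about 13% to 19% (0.36² = 0.13, 0.44² = 0.19), not 25%.

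**4. Simulation on the protocol's dose steps.** Baseline is cut at 443 mg, cumulative steps run from 3 to 4443 mg, and there is a top category for no reaction. The arms are 30 v 10 with a true 10-fold effect. The DBPCFC2 SD is not in the documents, so both 0.93 and 1.22 log10 are shown.

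| Setting | rho 0.3 | rho 0.5 | rho 0.7 |
|---|---|---|---|
| SD 0.93: rank-sum v Quade | 0.78 v 0.81 | 0.78 v 0.86 | 0.79 v 0.95 |
| SD 1.22: rank-sum v Quade | 0.55 v 0.56 | 0.59 v 0.65 | 0.66 v 0.79 |
| SD 1.22: rank-sum v linear ANCOVA | 0.57 v 0.60 | 0.59 v 0.67 | 0.65 v 0.83 |

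If rho applies after the eligibility cut, SD 1.22 gives 0.53 v 0.63 at rho 0.5 and a gain of up to about 23 points at rho 0.7. Across settings the gain is about 1-4, 5-10 and 13-23 points at rho 0.3, 0.5 and 0.7. With 25 v 9 analysed and rho 0.5, power is 0.73 v 0.81 (SD 0.93) or 0.53 v 0.59 (SD 1.22). Type I error stays near 0.05 throughout.

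**5. Larger effects.** Section 15.5 expects 75% desensitized at DBPCFC2, and section 3.1.1 counts an ED below 1443 mg there as failure. In the SD 0.93 model at rho 0.5, a 10-fold shift puts about 32% of the active arm at 1443 mg or above, and a 30-fold shift about 53%. The plan's assumption therefore points to 30-fold or more. At 30-fold and rho 0.5, power is 0.985 v 0.993 (SD 0.93, Quade) or 0.89 v 0.95 (SD 1.22, linear ANCOVA). Over rho 0.3-0.5 and effects of 30-fold or more, the gain is about 0-2 points with SD 0.93 and 1-6 with SD 1.22.

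**The case against.** The strongest reply is that the gain is small where the plan expects to be. At the effects implied by 75% desensitization, power is already high and adjustment adds a few points at most. Desensitization also needs the other two criteria. At a true 10-fold shift the 10-fold criterion is itself met in only about 66% of simulated trials, so joint success on the two ED criteria rises from about 0.56 to 0.61, by 5 points. The objective is secondary, and section 9.1 uses the placebo arm mainly for adverse events. All of this stands and limits the weight of the point.

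A reader might also infer more than the documents support:

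- *That the comparison is biased or invalid.* It is not. The arms are randomised and the unadjusted test holds its level.
- *That the plan chose an unadjusted method or ignores baseline.* Section 9 is silent on ED, so adjustment is unspecified rather than ruled out. The 10-fold criterion and the change endpoint do use DBPCFC1.
- *That this is the only randomised clinical comparison.* Accidental-ingestion reactions are also compared by arm; the point is confined to challenge ED.
- *That a 2.2-fold baseline imbalance reaches DBPCFC2 in full.* It carries over only in proportion to rho.
- *That the skin-test endpoint, "The change in ED of end-point dilution skin testing between actively treated and placebo treated participants following maintenance therapy", has the same measurable loss.* Section 3.1.2 names a change but no analysis, and the documents give no figure from which to size a loss.

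**Conclusion.** The point holds as a modest efficiency gain left unused. As worded, the between-arm ED criterion has no baseline term, and nothing in section 9 adds one. Adjustment raised power in every 10-fold setting tried, but the amount rests on a correlation and a DBPCFC2 spread that the documents do not give. It also assumes that the spread in section 1.6.1, from children aged 3 to 18, carries over to this trial's participants aged 7 to 55. The gain matters most if the true effect is near 10-fold and rho is 0.5 or more. Starting power there is about 0.8 with SD 0.93, and about 0.53 to 0.66 with SD 1.22 over rho 0.3-0.7. It is slight if rho is near 0.3 or the effect is 30-fold or larger. The primary Treg analysis is unaffected.

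**What to change.** In sections 2.2.1 and 9, state that the between-arm comparison of DBPCFC2 ED will use a rank-based ANCOVA (Quade), or an ordinal model that respects the dose steps and the 4443 mg ceiling, with arm as factor and DBPCFC1 ED as covariate. Keep reporting unadjusted medians by arm. A raw change from DBPCFC1 is not a substitute: with equal SDs its variance factor is 2(1 − rho), which at rho 0.3 is 1.4, worse than no adjustment (1), against 0.91 for ANCOVA.

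The cost is one degree of freedom and a wording change, made by amendment if section 9.4 is taken to apply. No new data are needed. Adjustment does not settle how participants without a DBPCFC2 ED are counted; that needs its own sentence.
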